3.2 Secondary Endpoints

Time to progression of disease

4. STUDY DESIGN

4.1 Overview of Study Design

Treatment regimen

Alternating ixazomib 4.0 mg po on days 1, 8 and 15 per each 28- day cycle for two consecutive cycles, followed by then lenalidomide 10 mg po daily for two consecutive cycles until disease progression, intolerable toxicity or maximum of 24 cycles of therapy. Dose reduction for toxicity will be incorporated. If >30 days off initially planned next cycle of therapy, then patient will be taken off study. Toxicity will be graded per CTCAE version 4.0.

Therapy will start 30-120 days post autologous transplant when the patient is recovered from acute toxicity. See study flow chart on page 4 for scheduling of events for study.

4.2 Number of Patients

Thirty patients. First day of treatment will define enrolled on study therapy.

4.3 Duration of Study

Enroll 30 patients over 2-3 years with then two year follow-up of last patient who started treatment on the study.

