
Study Population:

Adult Autologous Multiple Myeloma Transplant patients

Duration of Study:

Five years (2-3 years to enroll patients on study)

Fred Hutchinson Cancer Research Center
Clinical Study Protocol [FHCRC 9266]

SCHEDULE OF EVENTS

Study Flow Chart

(Each cycle is 28 days) Cycle			1-4 cycles			5-24 cycles			
Day	Screening (Baseline within 30 days)	Predose Day (within 3 days) to Day 1 of Cycle 1-4	Day 8 (+/- 3 days) Week one	Day 15 and 22 (+/- 3 days) Weeks 2 and 3	Predose Day (within 3 days) to Day 1 of Cycle 5-24	Day 8 (+/- 3 day) Week one	Day 15 (+/- 3 days) Week 2	End of Study (Labs within 7 days and other tests within month after last dose of drug)	Survival Follow-up
Phase	Screening	Pretreatment	Treatment	Treatment		Treatment	Treatment	Post- Treatment	Post- Treatment
Study Procedures									
Obtain study informed consent		X							
Demographics		X							
Review Inclusion/Exclusion criteria		X							
Review/collect prior medications		X							
Collect medical history		X							
Enroll Revlimid REMS TM program pre cycle 3			X						
Safety Labs/ Measurements									
Collect serum β -hCG pregnancy test ^b	X	X ^b							
Collect CBC	X	X	X	X	X	X	X	X	X
Collect blood chemistry	X	X	X	X	X	X		X	X
Collect PT/INR & aPTT ^a	X								
Collect urinalysis (complete)	X								
Collect 24-hour urine creatinine clearance	X								

Fred Hutchinson Cancer Research Center
Clinical Study Protocol [FHCRC 9266]

Cycle	-----	1-4			5-24			-----
Day	Screening (Baseline) Within 30 days prior to first dose	Predose Day (within 3 days Day 1 of Cycle 1-4)	Day X (+/- 3 days) Week one	Day X Cycle 1-24	Pre dose within 3 days	Day X (+/- 3 days) Week one	Day X (+/- 3 days) Week 2	End of Study (within month after last dose of drug) Survival Follow-up
Phase	Screening	Pretreatment	Treatment	Treatment	Treatment	Treatment		Post-treatment Post-Treatment
Review concomitant medications	X	X			X			
Review adverse experiences		X			X			X
ECOG Performance Status	X	X			X			X X
Perform physical examination and collect vital signs (including height at screening and weight at all visits)	X	X			X			X X
Efficacy Measurements								
MRI Bone Marrow and osseous survey								X X (yearly)
BM aspirate and biopsy unilateral for pathology, flow, cytogenetics and myeloma FISH panel	X							X X (yearly)
Serum free light or SPEP with IF	X			X (every 3 months)				X X (every 3 months)

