2.2 Secondary Objectives

- Evaluate the ability to deliver the planned therapy
- Assess initial response to therapy
- Evaluate the median time to disease progression
- Assess overall survival

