7.1.1 Determination of Sample Size

Thirty Multiple Myeloma patients post ASCT are to be enrolled over 2-3 years. Expect to enroll 1-1.5 patients per month.

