7.1.6 Efficacy Analysis

An endpoint of the study is time to disease progression. Patients will be followed for initial response and for progression of disease. Response criteria will be determined by International Myeloma Working Group Criteria. In patients with chemo-refractory disease at the time of ASCT, the therapy will be felt to be promising if median time to progression is >9 months. If chemo-sensitive disease at time of ASCT the therapy will be felt to be promising if median time to progression is > 41 months based on CALGB 10014 lenalidomide maintenance study post ASCT. Initial response rates and outcome will be descriptively reported. Patients will be followed for overall survival.

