8.2 Procedures for Reporting Serious Adverse Events

AEs may be spontaneously reported by the patient and/or in response to an open question from study personnel or revealed by observation, physical examination, or other diagnostic procedures. Any clinically relevant deterioration in laboratory assessments or other clinical finding is considered an AE. When possible, signs and symptoms indicating a common underlying pathology should be noted as one comprehensive event. For serious AEs, the investigator must determine both the intensity of the event and the relationship of the event to study drug administration. For serious pretreatment events, the investigator must determine both the intensity of the event and the relationship of the event to study procedures.

AEs which are serious must be reported to Millennium Pharmacovigilance (or designee) from the first dose of study drug through 30 days after administration of the last dose of ixazomib. Any SAE that occurs at any time after completion of ixazomib treatment or after the designated follow-up period that the sponsor-investigator and/or sub-investigator considers to be related to any study drug must be reported to Millennium Pharmacovigilance (or designee). In addition, new primary malignancies that occur during the follow-up periods must be reported, regardless of causality to study regimen, for a minimum of three years after the last dose of the investigational product, starting from the first dose of study drug. All new cases of primary malignancy must be reported to Millennium Pharmacovigilance (or designee).

Planned hospital admissions or surgical procedures for an illness or disease that existed before the patient was enrolled in the trial are not to be considered AEs unless the condition deteriorated in an unexpected manner during the trial (e.g., surgery was performed earlier or later than planned). All SAEs should be monitored until they are resolved or are clearly determined to be due to a patient's stable or chronic condition or intercurrent illness(es).

Since this is an investigator-initiated study, the principal investigator [name] [name] also referred to as the sponsor-investigator, is responsible for reporting serious adverse events (SAEs) to any regulatory agency and to the sponsor- investigator's EC or IRB.

**Fred Hutchinson Cancer Research Center
Clinical Study Protocol [FHCRC 9266]**

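### Follow-up planned to 24 months after the last start is too short to judge a median time to progression above 41 months in chemo-sensitive patients

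*Combined protocol and SAP*

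**What the plan says.** Section 4.2 fixes the sample and the start of the clock on study: "Thirty patients. First day of treatment will define enrolled on study therapy". Section 4.3 sets the observation period: "Enroll 30 patients over 2-3 years with then two year follow-up of last patient who started treatment on the study". The protocol summary gives a total duration of five years. Section 7.1.1 adds an accrual rate: "Expect to enroll 1-1.5 patients per month".

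Section 2.2 lists as a secondary objective: "Evaluate the median time to disease progression". Section 3.2 names TTP as the secondary endpoint. For chemo-sensitive disease, Section 7.1.6 calls the regimen "promising if median time to progression is > 41 months based on CALGB 10014 lenalidomide maintenance study post ASCT". For chemo-refractory disease the bar is 9 months.

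The plan gives no start point for TTP, censoring rule, estimator, confidence interval, test, power or expected number of chemo-sensitive patients. The Study Flow Chart has a survival follow-up column with serum myeloma tests every three months and yearly marrow, imaging and urine tests, without an end date. Section 8.2 requires reporting of new malignancies "for a minimum of three years after the last dose of the investigational product". Neither is linked to the 41-month criterion.

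**The concern.** The bar stands at 41 months, but the last patient is promised only 24 months of observation. When few patients can be watched as far as the bar, the Kaplan-Meier curve near 41 months rests on a handful of people, and it may not have fallen to one half by the data cut-off. The median is then reported as not reached. The plan does not say whether that satisfies the criterion.

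The effect is perverse: the better the regimen works, the less often the quantity named in the objective can be estimated. Potential efficacy is one of the conditions in Section 7.1.8 for designing a phase III trial, so an ambiguous reading could feed that decision.

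**Working it through.** **Inputs from the protocol.** 30 patients (4.2); accrual of 24 to 36 months, then 24 months after the last start (4.3); five years in total (summary); 1 to 1.5 patients per month (7.1.1); bar of 41 months (7.1.6).

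**Assumptions, because the plan is silent.** TTP counted from first treatment; uniform accrual; exponential TTP; no dropout; 20 to 30 chemo-sensitive patients.

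**Step 1: the plan's own duration.** 36 + 24 = 60 months reproduces the five years. With two-year accrual, 24 + 24 = 48 months. The stated rate gives 30/1.5 = 20 to 30/1 = 30 months of accrual, so accrual A is taken from 20 to 36 months.

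**Step 2: potential follow-up.** It is uniform from 24 to 24 + A months, so the share under 41 months is (41 − 24)/A = 17/A.

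**Step 3: number at risk at 41 months.** With a true median of 41 months, half are progression-free then: n × (1 − 17/A) × 0.5.

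**Step 4: share actually censored before 41 months.** Average 2^(−u/41) over follow-up times u from 24 to 41: (41/ln 2) × (2^(−24/41) − 0.5)/A = 59.15 × 0.1665/A = 9.85/A.

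**Step 5: how often the Kaplan-Meier median is not reached.** Simulation, 20,000 trials per setting, n = 20, 25 and 30.

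| Accrual (months) | Follow-up under 41 months | At risk at 41 months, n = 20 / 30 | Censored before 41 months | Not reached, true median 41 | Not reached, true median 55 |
|---|---|---|---|---|---|
| 20 | 85% | 1.5 / 2.3 | 49% | 49–50% | 75–78% |
| 24 | 71% | 2.9 / 4.4 | 41% | 40–43% | 68–70% |
| 30 | 57% | 4.3 / 6.5 | 33% | 28–32% | 59–60% |
| 36 | 47% | 5.3 / 7.9 | 27% | 19–24% | 49–51% |

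The at-risk and censored columns are for a true median of 41 months. Evenly spaced instead of random start dates lower the smallest not-reached figure to 18%.

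With 24-month accrual and a true median of 41 months, about 80% of results above 41 months are simply medians not reached. Even if all 30 patients were chemo-sensitive, the 95% upper limit for the median would be finite in only 7% to 17% of trials (accrual of 24 to 36 months).

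**Step 6: length needed.** For every patient to have 41 months, the study must run A + 41 = 61 to 77 months from the first start. Section 4.3 gives 48 to 60.

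**Step 7: other readings.** If five years is a fixed end date and accrual takes 24 months, follow-up runs from 36 to 60 months. The share under 41 months is 5/24 = 21%, and the median is not reached in 14% to 18% of trials at a true median of 41 months. With 36-month accrual the two readings coincide. If TTP runs from transplant, follow-up gains about 1 to 4 months, and the share becomes 16/24 to 13/24 (67% to 54%) or 16/36 to 13/36 (44% to 36%).

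**The case against.** A reader might infer that most patients would be censored before 41 months. The documents do not support that. Patients who progress before the cut-off are events, and at a true median of 41 months only 27% to 49% are censored before the bar. Nor is it always a majority who lack the potential follow-up: with 36-month accrual, 53% can be observed to 41 months.

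A reader might also infer that the phase III decision would hang on the tail of this curve. Section 7.1.8 also asks for acceptable toxicity and for event-free survival consistent with historical benchmarks. The primary endpoint is toxicity, and TTP is secondary with no stated test or power. Nor does the plan say that a median not reached counts as promising. The fault is that it leaves this open.

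The best counter-argument is that observation may not stop where Section 4.3 says. The summary's five years could be a fixed end date, the flow chart's post-treatment myeloma tests have no end, and overall survival follow-up has none either. This makes the documents ambiguous and could shrink the problem. It does not remove it, because nothing states that progression is followed to 41 months in every chemo-sensitive patient. The malignancy reporting in Section 8.2 is a reporting duty, not a schedule of myeloma tests.

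The 24-month proportion proposed below also has limits. At 67% its 95% half-width is 1.96 × √(0.667 × 0.333/n), about 21 points for n = 20 and 17 for n = 30. A constant hazard with the 27-month placebo median in Table 1.7 would give 2^(−24/27) = 54%, which lies inside that margin. The proportion is a cleaner description, not a powerful test.

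**Conclusion.** The concern holds in this form: the follow-up in Section 4.3 does not fit the 41-month bar in Section 7.1.6. About 47% to 85% of patients have potential follow-up under 41 months, about 1.5 to 8 chemo-sensitive patients would be at risk there, and the median would not be reached in about 18% to 50% of trials at a true median of 41 months and about 50% to 78% at 55 months. The first range needs only uniform accrual over 20 to 36 months. The others also need exponential TTP, no dropout and 20 to 30 chemo-sensitive patients. Dropout, for which the plan gives no rate, would worsen them.

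On the fixed five-year reading with 24-month accrual the share falls to about 21%. The 9-month chemo-refractory criterion lies well inside the 24-month minimum and is unaffected. Because this is a secondary benchmark without a power claim, the plan should be changed, but the primary toxicity assessment is not in question.

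**What to change.** In Section 7.1.6:

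- Define the start point of TTP and the censoring rule.
- Base the chemo-sensitive efficacy statement on the Kaplan-Meier proportion progression-free at 24 months, with a confidence interval. Set it against the value implied by the 41-month bar, 2^(−24/41) = about 67%, and state that this assumes a constant hazard.
- Report the median descriptively, with the number at risk at 41 months.
- State that a median not reached because of too little follow-up does not meet the 41-month criterion.

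In Section 4.3:

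- State that progression dates continue to be collected through the existing survival follow-up column of the flow chart, and say whether the five years is a fixed end date.
- Compare the median with 41 months only once the last chemo-sensitive patient has passed 41 months.

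The cost is an amendment to two sections. The 24-month proportion needs no follow-up beyond what Section 4.3 already plans, and later progression dates use tests already in the flow chart. The downsides are an imprecise 24-month estimate (half-width of about 17 to 21 points) and a later final median.

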5. STUDY POPULATION

5.1 Inclusion Criteria

Each patient must meet all of the following inclusion criteria to be enrolled in the study:

1. Male or female patients 18 years or older.
 - a. Eastern Cooperative Oncology Group (ECOG) performance status and/or other performance status 0, 1, or 2.
 - b. Any autologous patient who underwent high dose Melphalan (≥ 140 mg/m²) therapy/PBSC rescue for any stage of Multiple Myeloma and did not participate in another clinical transplant trial whose primary endpoint is also evaluating long-term, disease-free survival or survival. Consenting for study between 30 days to 120 days after transplant. Earliest can start therapy is 30 days post transplant after recovered from acute toxicity of ASCT.
2. Voluntary written consent must be given before performance of any study related procedure not part of standard medical care, with the understanding that consent may be withdrawn by the patient at any time without prejudice to future medical care.
3. Female patients who:
 - a. Are postmenopausal for at least 1 year before the screening visit, OR
 - b. Are surgically sterile, OR
 - c. If they are of childbearing potential, agree to practice 2 effective methods of contraception, at the same time, from the time of signing the informed consent form through 90 days after the last dose of study drug, OR
 - d. Agree to practice true abstinence when this is in line with the preferred and usual lifestyle of the subject. (Periodic abstinence [e.g., calendar, ovulation, symptothermal, post-ovulation methods] and withdrawal are not acceptable methods of contraception.)

**Fred Hutchinson Cancer Research Center
Clinical Study Protocol [FHCRC 9266]**

4. Male patients, even if surgically sterilized (i.e., status post-vasectomy), must agree to one of the following:
 - a. Agree to practice effective barrier contraception during the entire study treatment period and through 90 days after the last dose of study drug, OR
 - b. Agree to practice true abstinence when this is in line with the preferred and usual lifestyle of the subject. (Periodic abstinence (e.g., calendar, ovulation, symptothermal, post-ovulation methods] and withdrawal are not acceptable methods of contraception.)
5. Patients must meet the following clinical laboratory criteria:
 - a. Absolute neutrophil count (ANC) $\geq 1,000/\text{mm}^3$ and platelet count (transfusion independent) $\geq 75,000/\text{mm}^3$.
 - b. Total bilirubin $\leq 1.5 \times$ the upper limit of the normal range (ULN).
 - c. Alanine aminotransferase (ALT) and aspartate aminotransferase (AST) $\leq 3 \times$ ULN.
 - d. Calculated creatinine clearance $\geq 30 \text{ mL/min}$ (see appendix).

5.2 Exclusion Criteria

Patients meeting any of the following exclusion criteria are not to be enrolled in the study:

1. Female patients who are lactating or have a positive serum pregnancy test during the screening period.
2. Failure to have fully recovered (i.e., \leq Grade 1 toxicity) from the reversible effects of prior ASCT chemotherapy.
3. Major surgery within 14 days before enrollment.
4. Radiotherapy within 14 days before enrollment. If the involved field is small, 7 days will be considered a sufficient interval between treatment and administration of the ixazomib.
5. History of central nervous system multiple myeloma involvement.
6. Infection requiring systemic antibiotic therapy or other serious infection within 14 days before study enrollment.
7. Evidence of current uncontrolled cardiovascular conditions, including uncontrolled hypertension, uncontrolled cardiac arrhythmias, symptomatic congestive heart failure, unstable angina, or myocardial infarction within the past 6 months.

**Fred Hutchinson Cancer Research Center
Clinical Study Protocol [FHCRC 9266]**

8. Systemic treatment, within 14 days before the first dose of ixazomib, with strong inhibitors of CYP1A2 (fluvoxamine, enoxacin, ciprofloxacin), strong inhibitors of CYP3A (clarithromycin, telithromycin, itraconazole, voriconazole, ketoconazole, nefazodone, posaconazole) or strong CYP3A inducers (rifampin, rifapentine, rifabutin, carbamazepine, phenytoin, phenobarbital), or use of Ginkgo biloba or St. John's wort.
9. Ongoing or active systemic infection, active hepatitis B or C virus infection, or known human immunodeficiency virus (HIV) positive.
10. Any serious medical or psychiatric illness that could, in the investigator's opinion, potentially interfere with the completion of treatment according to this protocol.
11. Known allergy to any of the study medications, their analogues, or excipients in the various formulations of any agent. Patient cannot be allergic to boron.
12. Known GI disease or GI procedure that could interfere with the oral absorption or tolerance of ixazomib including difficulty swallowing.
13. Diagnosed or treated for another malignancy within 2 years before study enrollment or previously diagnosed with another malignancy and have any evidence of residual disease. Patients with nonmelanoma skin cancer or carcinoma in situ of any type are not excluded if they have undergone complete resection.
14. Patient has \geq Grade 2 peripheral neuropathy, or Grade 1 with pain on clinical examination during the screening period.
15. Participation in other clinical trials, including those with other investigational agents not included in this trial, within 30 days of the start of this trial and throughout the duration of this trial.
16. Patients with history prior to transplant of progression on lenalidomide therapy.

6. STUDY DRUG

6.1 Description of Investigational Agents

Treatment regimen consists of alternating ixazomib 4.0 mg po on days 1, 8 and 15 per each 28- day cycle for two consecutive months, followed by then lenalidomide 10 mg po daily for two consecutive months until disease progression, intolerable toxicity or maximum of 24 months of therapy. Dose reduction for toxicity will be incorporated. If >30 days off initially planned next cycle of therapy, then the patient will be taken off study. Toxicity graded per CTCAE version 4. Patients will start therapy 30-120 days post autologous transplant.

6.1.1 Ixazomib Capsules

The ixazomib drug product is provided in strengths of 4.0-, 3.0-, and 2.3-mg capsules as the active boronic acid. The different dose strengths are differentiated by both capsule size and color

**Fred Hutchinson Cancer Research Center
Clinical Study Protocol [FHCRC 9266]**

as described below:

Dose Strength	Capsule Size	Capsule Color
4.0 mg	Size 4	Ivory
3.0 mg	Size 3	Light gray
2.3 mg	Size 2	Light pink

For additional details, please see the ixazomib IB.

6.2 Study Drug Administration of Ixazomib

Ixazomib is stored in the IDS Pharmacy according to storage conditions detailed in the Investigator's Brochure and is dispensed by IDS Pharmacy for each cycle. Patients will keep diary to show took drugs. Patients should be instructed to swallow ixazomib capsules whole, with water, and not to break, chew, or open the capsules. Study drug should be taken on an empty stomach (no food for 2 hours before and 1 hour after dosing). Each capsule should be swallowed separately with a sip of water. A total of approximately 8 ounces (240 mL) of water should be taken with the capsules.

Missed doses can be taken as soon as the patient remembers if the next scheduled dose is 72 hours or more away. A double dose should not be taken to make up for a missed dose. If the patient vomits after taking a dose, the patient should not repeat the dose but should resume dosing at the time of the next scheduled dose.

6.2.1 Ixazomib Administration

All protocol-specific criteria for administration of study drug must be met and documented before drug administration. Study drug will be administered or dispensed only to eligible patients under the supervision of the investigator or identified subinvestigator(s). Patients should be monitored for toxicity, as necessary, and doses of ixazomib should be modified as needed to accommodate patient tolerance to treatment; this may include symptomatic treatment, dose interruptions, and adjustments of ixazomib dose (see Section 9.3).

Capsules of ixazomib will also be referred to as study drug. Study drug will be supplied by Millennium as capsules of 2.3-, 3.0- and 4.0 mg ixazomib. This is dependent on available ixazomib formulation.

The prescribed administration of ixazomib doses in this study is 4 mg ixazomib on days 1, 8 and 15 of each 28 day cycle for two cycles in a row followed then by lenalidomide therapy for two 28 day cycles for a total of 24 months of therapy.

